9.5.7 Injection Site Local Tolerability Assessment Data

Injection-site assessment data will be listed and summarized in frequency tables by treatment, age group and timepoint.

9.5.8 Pain measurements Using the Visual Analog Scale (VAS)

Intensity of pain data at the injection site as soon as practicably possible after the injection, and at multiple postdose timepoints, as reported by the patient and measured according to the 0- to 100-mm visual analog scale will be listed and summarized by treatment and age group.

The time 0 (immediately after dosing) data will be analyzed separately by age group using the Wilcoxon signed-rank test. The difference in medians between LY900014 and Humalog and the 95% CIs for the difference will be presented.

VAS data will also be summarized based on the following categories of score: 0, 1-10, 11-20, 21-30, 31-40, etc up to the maximum category by treatment, age group and timepoint and also the categories ≤ 10 mm, ≤ 20 mm and ≤ 45 mm. The table will show number and percent of patients with observations in each category.

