##### **10.3.1.2.1. Statistical Evaluation of the Intensity of Injection-Site Pain**

The primary study assessment will be the intensity of pain at each injection site immediately after the injection (time 0) as reported by the subject and measured according to the 0- to 100-mm VAS.

A mixed-effect model will be used to analyze the time 0 (immediately after dosing) data separately by age group, using the statistical model that includes treatment, sequence, and period as fixed effects and subject within sequence as a random effect. It is possible that VAS scores will be zero; hence if the distribution of the data implies that a log transformation is required then the score may be updated to  $\log(\text{VAS}+1)$  to allow for the inclusion of the 0 values in the analysis.

A descriptive summary will be provided for the following categories of scores: 0, 1-10, 11-20, 21-30, 31-40, etc. up to the maximum category by treatment for each time point.

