3. INTRODUCTION

This SAP has been developed after review of the Clinical Study Protocol (final version dated 08 December 2016), amendment (a) (dated 09 March 2017), amendment (b) (dated 24 May 2017) and amendment (c) (dated 04 August 2017).

This SAP describes the planned analysis of the safety, tolerability, pharmacokinetic (PK) and glucodynamic (GD) data from this study. A detailed description of the planned TFLs to be presented in the clinical study report (CSR) is provided in the accompanying TFL shell document.

The intent of this document is to provide guidance for the statistical and PK analyses of data. In general, the analyses are based on information from the protocol, unless they have been modified by agreement between Eli Lilly and Company and CCI. A limited amount of information concerning this study (e.g., objectives, study design) is given to help the reader's interpretation. This SAP must be signed off prior to first patient administration for this study. When the SAP and TFL shells are agreed upon and finalized, they will serve as the template for this study's CSR.

This SAP supersedes the statistical considerations identified in the protocol; where considerations are substantially different, they will be so identified. If additional analyses are required to supplement the planned analyses described in this SAP, they may be performed and will be identified in the CSR. Any substantial deviations from this SAP will be agreed upon between Eli Lilly and Company and CCI and identified in the CSR. Any minor deviations from the TFLs may not be documented in the CSR.

This SAP is written with consideration of the recommendations outlined in the International Council on Harmonisation (ICH) E9 Guideline entitled Guidance for Industry: Statistical Principles for Clinical Trials¹ and the ICH E3 Guideline entitled Guidance for Industry: Structure and Content of Clinical Study Reports².

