9.3.2 Pharmacokinetic Statistical Inference

Log-transformed C_{max} , AUC(0-30min), AUC(0-1h), AUC(0-10h), AUC(2-10h), AUC(0- t_{last}), AUC(0-inf), CL/F and V_z/F for insulin lispro will be evaluated to estimate least-squares geometric means, ratios of geometric means between LY900014 and Humalog (reference), and their corresponding 95% CIs for each age group separately using the statistical model that includes treatment, sequence, and period as fixed effects and patient within sequence as a random effect.

Example SAS code:

```
proc mixed data=pk;
class patient period treatment sequence ;
model logpk = treatment period sequence / ddfm=kr;
random patient(sequence);
lsmeans treatment;
run;
```

The same model without log-transformation will be used for the analysis of the PK time parameters (early 50% t_{max} , late 50% t_{max} , t_{max} , and $t_{1/2}$). Least-squares means, treatment differences in least-squares means, and the corresponding 95% CIs for the treatment differences will be estimated from the model. The treatment ratios and 95% CIs for the ratios will be calculated using Fieller's Theorem (Chow and Liu 2009³).

All analyses will be repeated for the population of patients who complete the study.

An exploratory analysis on the interaction between treatment and age group will be assessed using data from both age groups by a model similar to that for each age group, with the addition of age group and the interaction of treatment by age group as fixed effects. This test will be used to compare whether the LY900014 versus insulin lispro treatment effect is similar between the elderly and younger adult groups. The analysis will include all PK parameters analysed previously (both untransformed and log-transformed PK parameters).

Example SAS code:

```
proc mixed data=pk;
class patient period treatment sequence agegrp;
model logpk = treatment period sequence agegrp agegrp*treatment /
ddfm=kr;
random patient(sequence);
lsmeans agegrp*treatment;
run;
```

As treprostinil plasma concentrations after administration of LY900014 are expected to be very low, a descriptive statistical analysis may be conducted if sufficient data are available for this analysis.

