9.4.2 Glucodynamic Statistical Inference

The GD parameters will be listed and summarized by treatment and age group.

The statistical model will be the same as the model used for the analysis of the PK parameters. The non-time variables will be log-transformed prior to analysis and will include R_{max} , G_{tot} , $G_{\text{tot}}(0-30\text{min})$, $G_{\text{tot}}(0-1\text{h})$, and $G_{\text{tot}}(0-10\text{h})$. For GD parameters that have at least 1 patient with a value equal to zero, a value equal to the smallest non-zero observed GD value for that parameter divided by 2 will be added to all values, and the analysis of the log-transformed data will be performed.

The same model without log-transformation will be used for the analysis of the GD time parameters (T_{onset} , TR_{max} , early 50% TR_{max} , and late 50% TR_{max}). Least-squares means, treatment differences in least-squares means, and the corresponding 95% CIs for the treatment differences will be estimated from the model. The treatment ratios and 95% CIs for the ratios will be calculated using Fieller's Theorem

All analyses will be repeated for the population of patients who complete the study.

An exploratory analysis on the interaction between treatment and age group will be assessed using data from both age groups by a model similar to that for each age group, with the addition of age group and the interaction of treatment by age group as fixed effects. This test will be used to compare whether the LY90014 versus insulin lispro treatment effect is similar between the elderly and younger adult groups. The analysis will include all GD parameters analysed previously (both untransformed and log-transformed GD parameters).

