11. CHANGES FROM THE PROTOCOL SPECIFIED STATISTICAL ANALYSES

The protocol originally planned to analyse PK time parameters using a log-normal model. This was updated to a linear model with Fieller methodology added. Non-parametric analysis of the PK and GD data was originally planned in the protocol but this was removed for consistency with other studies. The VAS statistical analysis was updated to a non-parametric analysis due to issues observed in ITSC.

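### The SAP's signed-rank test of time 0 injection-site pain drops the protocol's period adjustment, which a rank-sum test on period differences would keep at little cost

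*SAP*

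**What the plan says.** Protocol 10.3.1.2.1 analyses the time 0 VAS score by age group with a mixed model, "using the statistical model that includes treatment, sequence, and period as fixed effects and subject within sequence as a random effect". It allows a log transformation with 1 added, because "It is possible that VAS scores will be zero".

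SAP 9.5.8 replaces this: "The time 0 (immediately after dosing) data will be analyzed separately by age group using the Wilcoxon signed-rank test". The estimate follows: "The difference in medians between LY900014 and Humalog and the 95% CIs for the difference will be presented". Neither sentence mentions period or sequence.

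Elsewhere the SAP keeps the adjustment. Section 9.3.2 uses a "statistical model that includes treatment, sequence, and period as fixed effects and patient within sequence as a random effect" for PK, and section 9.4.2 says of GD: "The statistical model will be the same as the model used for the analysis of the PK parameters".

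On departures from the protocol, SAP section 3 promises that "where considerations are substantially different, they will be so identified". Section 11 says of the pain analysis only this: "The VAS statistical analysis was updated to a non-parametric analysis due to issues observed in ITSC".

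**The concern.** In a two-period crossover, half the patients receive LY900014 first and half second. If pain scores shift between visits for any reason other than treatment, that shift enters the LY900014 minus Humalog differences with opposite signs in the two sequences. A model with a period term removes it. A signed-rank test on the pooled differences does not.

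Two things can follow. With balanced sequences the shift acts as extra noise, so the test is conservative and loses power. With unequal sequences part of the shift stays in the estimate as bias.

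The stated reason for the change, problems seen in ITSC, supports going non-parametric. It does not explain giving up the period adjustment. The stakes are modest: VAS pain is not among the endpoints in Protocol Table ITRR.1, and no power claim or decision rule rests on it. It is, however, the only measure in SAP 9.5 with a planned treatment test and confidence interval.

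**Working it through.** **Inputs.** From the documents: two sequences, up to 42 enrolled and at least 34 completing per age group, and two-sided alpha 0.05. The documents give no SD, effect size, period effect, share of zeros or power for VAS, so there is no plan figure to reproduce. Assumed: 21:21 allocation, random dropout, a treatment shift of 0.5 SD of the paired difference, and period effects of 0, 0.25 and 0.5 SD.

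**Step 1: how period enters.** Let d be the treatment shift and π the period effect (Period 1 minus Period 2). The expected LY900014 minus Humalog difference is d + π when LY900014 comes first and d − π when Humalog comes first. Averaged over patients:

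d + π(n1 − n2)/n

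At 17:17 the bias is zero, but pooling the two groups raises the variance of the differences from 1 to 1 + π² (in SD units). At π = 0.5 that is 1.25, so the standardised shift falls from 0.5 to 0.5/√1.25 = 0.447.

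**Step 2: likely imbalance.** With 8 of 42 dropping out and none replaced, the probability that k come from one sequence is C(21,k)·C(21,8−k)/C(42,8).

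| Completers | Probability | Bias as a share of π |
|---|---|---|
| 17:17 | 30% | 0 |
| 18:16 | 46% | 2/34 = 5.9% |
| 19:15 | 19% | 4/34 = 11.8% |
| 20:14 or worse | 4.5% | 6/34 = 17.6% at 20:14 |

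The mean bias is 5.8% of π.

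**Step 3: the adjusted alternative.** Take Period 1 minus Period 2 for each patient. Its expectation is π + d for LY900014-first and π − d for Humalog-first. The sequences differ by 2d and π cancels. A Wilcoxon rank-sum test between sequences therefore tests treatment with period removed, and half the Hodges-Lehmann shift estimates d.

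**Step 4: power.** Simulation with normal differences, n = 34 and 20,000 runs per cell; signed-rank against rank-sum:

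| Period effect | 17:17 | 18:16 (range over direction of π) | Averaged over splits and directions |
|---|---|---|---|
| 0 | 79.2% vs 78.8% | 79.3% vs 79.2% | 79% vs 79% |
| 0.25 SD | 77% vs 78–79% | 74–79% vs 78–79% | 77% vs 78% |
| 0.5 SD | 71% vs 78% | 64–76% vs 79% | 70% vs 78% |

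The averages use the 20:14 figures for 20:14 or worse. Signed-rank type I error was 2.6% to 5.0% at every split through 20:14, so false positives are not inflated. Separate repeat simulations agreed to within about 1 point on power.

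**Step 5: cost when there is no period effect.** The rank-sum loses 0.1 to 0.4 points at 17:17 or 18:16, 1.5 at 19:15 and 2.0 at 20:14 on normal data. With heavy tails (t, 3 df) it is 85.1% vs 84.4% at 17:17 and 84.9% vs 82.4% at 20:14. With scores floored at zero (30% or 50% zeros on Humalog) at 17:17, it loses about 1 point with no period effect, gains 0.4 to 1.0 at 0.25 SD and gains 5 to 6 at 0.5 SD.

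**Step 6: the estimate.** SAP 9.5.8 does not say whether its median difference is the Hodges-Lehmann median of paired differences or the difference of the two treatment medians. Under the second reading the estimate is exactly 0 in 0.1–0.5% of significant signed-rank results at 10–30% zeros, 0.5–1.4% at 50% zeros and 8–16% at 60% zeros. The ambiguity matters only if most scores are zero.

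**The case against.** The best defence is that the planned test is acceptable and largely disclosed. It is unbiased with balanced sequences, and its type I error does not exceed 5.0% in any split through 20:14. Section 11 announces the non-parametric switch, 9.5.8 names the test, and a statistician knows that a signed-rank test takes no covariates. Pain is a tolerability measure on which nothing is decided. All of this stands, and it is why the point is minor.

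The benefit also depends on a period effect that the documents do not supply. Protocol 7.2.1 standardises injections: few injectors, a consistent depth and a similar time of day. At 0.25 SD the average gain is about 1 point. Protocol 5.2 also allows same-sequence replacement, which makes imbalance less likely than in Step 2. These points limit the size and do not remove the concern. The sponsor thought period worth adjusting for in its protocol pain model and in every PK and GD model, and Protocol 7.2.1 rotates the injection site between lower quadrants across the two periods.

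The cost of the alternative is small but not zero: up to about 2.5 points at 20:14 with heavy tails. At a stress-test split of 22:12 it reaches 2 to 5 points. There the signed-rank type I error rises to 6.8–14.4% for period effects of 0.3 to 1.0 SD on normal data. That split cannot arise from 21:21 allocation without replacement, so it carries no weight here.

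The table shells, which are not available, may define the estimate. The wording point is therefore secondary.

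**Conclusion.** The concern holds as an optional improvement. SAP 9.5.8 drops the protocol's period adjustment, section 11 does not say so, and the stated reason for going non-parametric does not require it. The analysis is not invalid: at or near sequence balance the consequence is lost power, not false positives.

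Averaged over the likely splits, the loss is about 1 point at a period effect of 0.25 SD and about 8 points at 0.5 SD (70% vs 78%). Bias averages 5.8% of whatever period effect exists. These figures rest on an assumed 0.5 SD treatment shift, assumed period effects, 21:21 allocation and 8 random dropouts without replacement. The textual finding rests on none of them.

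**What to change.** In SAP 9.5.8, within each age group, compute each patient's Period 1 minus Period 2 VAS difference at time 0 and compare the two sequences by Wilcoxon rank-sum test. Report half the Hodges-Lehmann shift (LY900014-first minus Humalog-first) with its 95% CI, also halved, as the treatment estimate.

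If the signed-rank test is kept, the minimum is two sentences: one in section 11 saying that the protocol's period adjustment was dropped and why, and one in 9.5.8 saying that the estimate and CI are the Hodges-Lehmann median of paired differences.

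The cost is SAP wording and a few lines of code. Both tests use only patients with both periods, so the change loses no data. The power cost with no period effect is the small loss given in Step 5 of the working.

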### 10.3. Statistical Analyses

Statistical analysis of this study will be the responsibility of Lilly.

The primary statistical analyses for PK will be conducted on those subjects who receive at least 1 dose of study drug and have measurable insulin lispro concentrations. The primary statistical analysis for GD will be conducted on those subjects who complete at least 1 clamp procedure. Supportive analyses will be done on the key parameters for the subjects who complete all treatment periods with evaluable data. Safety analyses will be conducted for all enrolled subjects who receive at least 1 dose of study drug, whether or not they complete all protocol requirements.

Any change in the data analysis methods described in the protocol will require an amendment only if it changes a principal feature of the protocol. Any other change to the data analysis

methods described in the protocol and the justification for making the change will be described in the study results.

Summary statistics (including number of subjects, mean, standard deviation or standard error, minimum, and maximum) will be presented for continuous variables. A linear mixed-effect model will be used for continuous variables unless otherwise stated in the below subsections. The primary comparison between LY900014 and insulin lispro for each age group will be performed using the model that includes treatment, sequence, and period as fixed effects, and subject within sequence as a random effect. Unless otherwise noted, all tests of treatment effects will be conducted at a 2-sided alpha level of 0.05, and CIs will be calculated at 95%, 2-sided.

An exploratory analysis on the interaction between treatment and age group will be assessed using data from both age groups by a model similar to that for each age group, with the addition of age group and the interaction of treatment by age group as fixed effects. This test will be used to compare whether the LY900014 versus insulin lispro treatment effect is similar between the elderly and younger adult groups.

Additional exploratory analyses of the data will be conducted as deemed appropriate. Study results may be pooled with the results of other studies for population PK analysis purposes to avoid issues with post-hoc analyses and incomplete disclosures of analyses.

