7. SAMPLE SIZE JUSTIFICATION

Up to 42 younger adult and 42 elderly patients may be enrolled to ensure that at least 34 patients in each age group complete the study. Thirty-four completing patients in each age group will provide approximately 95% power to demonstrate a 40% increase in the insulin lispro area under the plasma concentration-time curve from time zero to 30 minutes (AUC[0-30min]) between LY900014 and Humalog within each age group. Testing will be done at an alpha level of 0.05 with a 2-sided confidence interval (CI). The variability was estimated by analyzing a Lilly internal study that showed a log-scale standard deviation of within-patient difference in AUC(0-30min) of 0.5. Analysis of internal data showed a log-scale standard deviation of within patient difference in time to early half-maximal plasma concentration (early 50% t_{max}) of 0.5,

which provides approximately 95% power to show a 30% reduction in early 50% t_{max} , testing with an alpha level of 0.05 and a 2-sided CI.

In addition, the study is adequately powered to evaluate the GD parameters within each age group. There is approximately 80% power to detect a 20% decrease in both time to onset of insulin action (T_{onset}) and time to half-maximal GIR before TR_{max} (early 50% TR_{max}), and approximately 85% power to detect at least a 40% increase in total amount of glucose infused over 30 minutes ($G_{tot}[0-30min]$) and total amount of glucose infused over 1 hour ($G_{tot}[0-1h]$).

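### SAP 9.5.8 pairs a signed-rank test of VAS pain with a "difference in medians" that, read literally, is not the quantity the test evaluates, and names no estimator or CI method

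*SAP*

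**What the plan says.** SAP 9.5.8 gives the test: "The time 0 (immediately after dosing) data will be analyzed separately by age group using the Wilcoxon signed-rank test". The next sentence gives the estimate: "The difference in medians between LY900014 and Humalog and the 95% CIs for the difference will be presented". It does not say how the difference or its interval is computed, or what happens to patients with the same score in both periods.

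Protocol 10.3.1.2.1 had planned something else: "A mixed-effect model will be used to analyze the time 0 (immediately after dosing) data separately by age group". It also foresaw zeros: "It is possible that VAS scores will be zero". SAP 11 records the switch, "The VAS statistical analysis was updated to a non-parametric analysis due to issues observed in ITSC", without describing those issues or defining the new estimate. The SAP governs (SAP 3: "This SAP supersedes the statistical considerations identified in the protocol"), so the protocol model does not fill the gap. The significance level is in Protocol 10.3: "all tests of treatment effects will be conducted at a 2-sided alpha level of 0.05". The planned number of pairs is in SAP 7: "at least 34 patients in each age group complete the study".

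**The concern.** The signed-rank test asks whether the within-patient differences are symmetric about zero. The location estimate that goes with it is the Hodges-Lehmann pseudo-median of those differences, and the matching interval comes from inverting the test. The difference between two treatment medians depends only on the two marginal distributions and is in general another number when scores are skewed or pile up at zero.

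Safety and tolerability is a secondary objective, and VAS pain is the only assessment in SAP 9.5 that receives a test and a CI. If the table shows a small p-value beside an estimate of 0, or beside a CI that includes 0, a reader may conclude that pain did not differ when the paired test says that it did, or may not know which to believe.

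**Working it through.** The documents state no power, error rate or distribution for VAS pain, so there is no figure of the plan to reproduce. The check asks whether the two quantities can disagree, and whether the matching estimator cures this.

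**1. Counting argument (n = 34 from SAP 7; scores assumed).** Suppose 18 patients score 0 on both products and 16 score higher on LY900014.
- Each treatment has at least 18 zeros among 34 scores, so both medians are 0 and their difference is 0, whatever the 16 patients report.
- The signed-rank test drops the 18 zero differences. All 16 remaining signs are positive, so the exact two-sided p = 2 / 2^16 = 0.00003.

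**2. Two constructed datasets, n = 34.** The CI for the difference in medians is a paired percentile bootstrap, an assumption because the SAP names no method. The p-values are normal approximations. Dataset A has the pattern of step 1, and its approximate p is larger than the exact 0.00003.

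| | Medians, LY900014 / Humalog | Difference in medians (95% CI) | Signed-rank p | Hodges-Lehmann, all pairs (95% CI) |
|---|---|---|---|---|
| A: 18 pairs 0/0 | 0 / 0 | 0 (0 to 7) | 0.0004 | 4.5 (1.5 to 8.0) |
| B: no zeros | 26 / 23 | +3 (-8 to 3) | 0.00003 | -6.0 (-7.0 to -2.5) |

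On A's non-zero differences alone, the Hodges-Lehmann estimate is 11.5 (8.0 to 14.5). B shows that even the direction can differ.

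**3. Simulation, 4,000 trials per row, n = 34.** Assumed, not from the documents: skewed integer scores, log-scale SD 1.0 between and 0.5 within patients, a log shift for LY900014, and the same bootstrap CI. A disagreement is a trial where p < 0.05 and the CI excluding 0 do not coincide. The last column uses the Hodges-Lehmann CI on non-zero differences.

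| Zeros on reference | Log shift | Test p < 0.05 | Median-difference CI excludes 0 | Disagree, median difference | Disagree, Hodges-Lehmann |
|---|---|---|---|---|---|
| 4.5% | 0.25 | 39.4% | 5.4% | 35.4% | 12.0% |
| 4.5% | 0.5 | 92.3% | 40.9% | 52.8% | 6.1% |
| 24% | 0.25 | 38.1% | 5.0% | 34.4% | 11.4% |
| 24% | 0.5 | 90.7% | 42.1% | 49.8% | 5.7% |
| 52% | 0.25 | 30.6% | 2.4% | 29.2% | 7.0% |
| 52% | 0.5 | 84.5% | 29.2% | 57.9% | 5.1% |
| 67% | 0.25 | 24.2% | 0.1% | 24.2% | 4.3% |
| 67% | 0.5 | 73.6% | 2.8% | 71.0% | 4.2% |

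With no shift, the median-difference CI and the test disagree in about 5% of trials. Nearly all disagreements are a significant test beside a CI that includes 0. The Hodges-Lehmann remainder comes from ties and from limits falling exactly on 0.

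**4. When the estimate is exactly 0.** In separate simulations, also n = 34 with assumed distributions, the difference in medians was exactly 0 in 48% of significant trials at 60% v 55% zeros, in 28% at 55% v 50%, and in about 1% or less at 50% v 35% or fewer.

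**5. Whether naming Hodges-Lehmann is enough.** With all 34 pairs there are 34 × 35 / 2 = 595 pairwise averages. The lower 95% limit sits at position floor(34 × 35 / 4 - 1.96 × √(34 × 35 × 69 / 24)) + 1 = floor(297.5 - 114.6) + 1 = 183 in ascending order.
- With 18 zero differences and the rest positive, 18 × 19 / 2 = 171 averages are 0. Since 171 < 183, the lower limit is above 0.
- With 19 zero differences and the other 15 all positive, 19 × 20 / 2 = 190 averages are 0. Since 190 > 183, the lower limit is exactly 0, although the exact p = 2 / 2^15 = 0.00006.

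So if the test drops zero differences and the interval keeps them, the contradiction returns. In a further simulation (n = 34, 50-60% zeros, assumed distributions) the all-pairs CI contained or touched 0 in about 74-84% of significant trials, against 6-7% when the CI used the same non-zero differences as the test.

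**The case against.** The strongest reply is that the wording need not be taken literally. The sentence follows directly on a paired test, and the phrase may be shorthand for the paired location shift. The TFL shells that accompany the SAP are not among the documents and may settle it. That stands as a possibility. But nothing in the protocol or SAP redefines the phrase, and if it is shorthand, the estimator and interval are still unnamed and the same sentence repairs both.

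A reader might go further and infer that the plan discards the pairing and so loses the precision of the crossover. The documents do not support that: it depends on how the CI is built, which the SAP does not say, and a bootstrap that resamples patients keeps the pairs together.

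A reader might also take the simulated percentages as the expected rate of contradictory tables. They are not. The protocol says only that zeros are possible, not that half the scores will be zero, and both the score distributions and the bootstrap interval are assumptions.

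Finally, the consequence is small. VAS pain is not among the endpoints in Table ITRR.1, which lists AEs for safety and tolerability. Protocol 9.4.8.1 says that injection-site pain will generally not count as clinically significant. No decision rule rests on this test. The planned summaries and score categories, which include a category for 0, would let a careful reader see a zero-heavy distribution. All of this limits the importance of the point but does not remove the mismatch.

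**Conclusion.** The point holds as a mismatch in wording with a concrete remedy. On its plain reading, SAP 9.5.8 reports a quantity that the signed-rank test does not evaluate, and it leaves the estimator, CI method and zero handling unstated. A significant p-value can then sit beside a CI that includes 0 or, when about half or more of the scores are 0, beside an estimate of exactly 0. The counting argument needs only the 34 completers and an assumed pattern of scores. The simulated disagreement with a true shift (24-71%, falling to 4-12% with the matching estimator) shows plausible size only, under the assumptions listed.

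Two stronger conclusions should not be drawn. A reversed direction with a significant test is possible, as dataset B shows, but was rare in simulation (0-0.6%). And the point does not touch the PK or GD conclusions: it concerns only how the pain comparison is presented. It is worth correcting because the correction costs almost nothing.

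**What to change.** Replace the sentence on the difference in medians in SAP 9.5.8 with:

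> The Hodges-Lehmann estimate of the within-patient difference (LY900014 minus Humalog) and its 95% CI, obtained by inverting the signed-rank test, will be presented; zero differences and ties will be handled in the same stated way in the test, the estimate and the CI (for example, if zero differences are dropped from the test, the estimate and CI will be based on the non-zero differences and the number of zero differences will be reported).

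The clause on zero differences is essential, as step 5 of the working shows. The treatment medians remain as the descriptive statistics already planned. The cost is one SAP sentence and one change to the table shell, with no new data.
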